The Preliminary Application of Socket-shield Technique in Orthodontic Extraction and
Fixed Orthodontic Treatment

NCT06510621

January 2, 2024

1. Software and Statistical Significance

All statistical analyses will be conducted using SPSS statistical software version 20.0 (IBM Corp., Armonk, NY, USA). A significance level of $P < 0.05$ will be considered statistically significant for all tests.

2. Data Screening and Assumptions

Normality Testing: The Shapiro-Wilk (S-W) test will be used to assess the normality of the data distribution. This test is suitable for small to medium-sized samples and will determine whether the data within each group approximate a normal distribution.

Homogeneity of Variance: The F-test will be used to assess whether the variances of the test group and control group are homogenous, which is an assumption necessary for parametric tests such as the paired samples t-test. Homogeneity of variance will be assumed if the F-test yields a P-value > 0.05 .

3. Primary Analysis

Paired Samples T-Test: To compare outcomes between the test group and the control group, a paired samples t-test will be conducted. This test is chosen due to the paired nature of data collected, which allows for a direct comparison of each subject under different conditions. Results with a P-value < 0.05 will be considered statistically significant, indicating a meaningful difference between the two groups.

4. Adjustment for Multiple Comparisons

If multiple outcomes are analyzed simultaneously, the Bonferroni correction will be applied to adjust the significance threshold and control for the risk of Type I errors. The corrected P-value will be calculated by dividing the significance level (0.05) by the number of comparisons. This adjustment will ensure that the findings remain robust and reduce the likelihood of false-positive results.

5. Additional Statistical Analyses

For exploratory analysis and if data do not meet normality or variance assumptions, the following non-parametric tests may be applied as alternatives:

Wilcoxon Signed-Rank Test: To compare medians between paired groups if normality assumptions are not met.

Levene's Test: As an alternative check for homogeneity of variances, particularly if sample sizes are unequal.

6. Handling Missing Data

Missing data will be addressed by assessing the pattern and mechanism of missingness. If data are missing completely at random (MCAR), listwise deletion will be employed. However, if data are missing at random (MAR), multiple imputation will be applied to generate a complete dataset. The approach will depend on the proportion of missing data and its assumed mechanism.

7. Data Presentation

All data will be presented as mean \pm standard deviation (SD) or median and interquartile range (IQR) depending on the data distribution. P-values, confidence intervals (CIs), and effect sizes will be reported for primary and secondary outcomes to provide a comprehensive understanding of the treatment effects.

This Statistical Analysis Plan ensures that the data are analyzed rigorously, assumptions are checked, and adjustments are applied to mitigate the risk of errors, making the findings robust and clinically meaningful.

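### Normality is checked group by group, but the paired t-test rests on the within-pair differences, which the SAP never checks (minor)

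*SAP*

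**What the plan says.** Section 2 opens its normality paragraph generally: "The Shapiro-Wilk (S-W) test will be used to assess the normality of the data distribution". It then says what the test is for: it "will determine whether the data within each group approximate a normal distribution".

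Section 3 sets the primary analysis: "To compare outcomes between the test group and the control group, a paired samples t-test will be conducted". The stated reason is the pairing, "which allows for a direct comparison of each subject under different conditions".

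Section 5, on additional analyses, begins: "For exploratory analysis and if data do not meet normality or variance assumptions, the following non-parametric tests may be applied as alternatives". The Wilcoxon signed-rank test is listed there with the purpose "To compare medians between paired groups if normality assumptions are not met".

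Section 7 presents data as mean and SD or as "median and interquartile range (IQR) depending on the data distribution".

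No section mentions the within-pair differences.

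**The concern.** A paired t-test is a one-sample t-test on the differences, so the distribution that matters is that of the differences. Section 2 aims the SAP's only normality check elsewhere. The check can therefore misfire both ways. It can raise an alarm when the differences are perfectly normal, and it can stay silent when they are not.

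Two things are at stake. The assumption behind the primary test goes unexamined, although the SAP's closing statement says that assumptions are checked. And if a flag can lead to a different test, a misdirected check may decide which test carries the primary conclusion.

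**Working it through.** **The assumption.** For pair *i*, let d_i = test_i − control_i. The paired t statistic is mean(d) / (SD(d)/√n). Only the d_i enter it, so its normality assumption concerns d.

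**Inputs.** From the SAP: Shapiro-Wilk by group (Section 2), paired t-test (Section 3), Wilcoxon as alternative (Section 5), significance level 0.05 (Section 1). Assumed, because the SAP does not give them: n = 15, 20, 30 pairs, two-sided tests, Shapiro-Wilk judged at 0.05, and the distributions below. Power is at a shift of 0.7 SD of the differences. The SAP has no figure of its own to reproduce.

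**False alarms.** Each side = shared subject effect (standardised lognormal, sigma 0.8) + independent normal error with SD e. The subject effect cancels in d, so d is exactly normal. The within-pair correlation is 1/(1 + e²): 1/2 = 0.50 for e = 1.0, 1/1.25 = 0.80 for e = 0.5, 1/1.04 = 0.96 for e = 0.2. With 10,000 trials per cell:

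| Correlation | Flagged in either group, n = 15/20/30 | Flagged on differences |
|---|---|---|
| 0.50 | 25/30/41% | about 5% |
| 0.80 | 46/57/73% | about 5% |
| 0.96 | 67/80/93% | about 5% |

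The closer the pairing, the more false alarms. For comparison, with bivariate normal data at correlation 0.5 the group-wise flags are 9–10%, simply because two groups are tested.

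**Misses.** Subject effect normal with SD 2; the test side also receives a centred Exp(1) component; optional independent normal error with SD e on each side. The group-wise check flags about 10%, because the wide subject effect hides the skew. What a check on the differences would catch depends on the error. The skewness of d is 2/(1 + 2e²)^1.5, which is 2 for e = 0, 2/1.5^1.5 = 1.09 for e = 0.5, and 2/3^1.5 = 0.38 for e = 1.0.

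| Error SD per side | Flagged on differences, n = 15/20/30 |
|---|---|
| 0 | 67/84/97% |
| 0.5 | 20/29/41% |
| 1.0 | 8/10/11% (about 7–13% with simulation error) |

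The rows with error rest on 2,000 trials per cell.

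**Effect on conclusions.** Suppose Wilcoxon replaces the t-test whenever either group is flagged.

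- Normal differences: type I error 0.046–0.055, against 0.046–0.054 for always using the t-test. The largest power losses are at correlation 0.96: 0.712 − 0.695 = 0.017, 0.845 − 0.830 = 0.015 and 0.962 − 0.955 = 0.007 for n = 15, 20 and 30.
- Skewed differences, no error: type I error for the mean 0.094/0.090/0.080, against 0.091/0.085/0.071. The largest gap is 0.080 − 0.071 = 0.009.

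So type I error moves by less than 0.01 and power falls by at most about 2 points.

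**The case against.** Three arguments deserve weight.

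First, the opening sentence of the normality paragraph is general and could cover the differences. The next sentence narrows it to the groups, so this does not rescue the text.

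Second, the t-test tolerates moderate non-normality, and the consequences calculated above are close to nil. This stands, and it is why the point is minor. It does not make the stated check the right one.

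Third, Section 3 is headed as the primary analysis and says without condition that "a paired samples t-test will be conducted", while Wilcoxon sits among the additional analyses. On that reading the primary test is already fixed and the group-wise check changes no inference. This is a fair reading, so the wording of the fallback is an ambiguity and not a definite error. It arises only if Section 5 is taken to allow replacement.

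A reader might also infer more than the SAP supports:

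- *That no fallback exists.* One is named; it is only worded as optional.
- *That the sponsor may pick whichever test is significant.* The SAP does not say so. Even if it were done at correlation 0.96, type I error would be 0.055/0.057/0.061 against 0.051.
- *That non-normal differences would generally be caught by a check on the differences and missed by the group-wise one.* The 67–97% figure assumes no measurement error. With error SD 1.0 per side the contrast is nearly gone.

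**Conclusion.** The target of the normality check is wrong as written: the paired t-test needs the differences to be approximately normal, and the SAP checks each group instead. This follows from the text and needs no simulation. Severity is minor.

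The false-alarm result is the firmer of the two. The size of the miss result depends heavily on measurement error. All magnitudes rest on assumed sample sizes and distributions. They do not support a claim that the primary inference is invalid or materially distorted.

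The optional wording in Section 5 is a secondary ambiguity about which test decides after a flag.

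**What to change.** - **Section 2:** assess normality on the within-pair (test minus control) differences, with a Q-Q plot and the Shapiro-Wilk test. Keep the group-wise look only for choosing the Section 7 summaries, where it is suitable.
- **Sections 3 and 5:** state in advance which test carries the primary conclusion. The simplest choice is to keep the paired t-test as primary whatever the preliminary test shows, and to report the Wilcoxon signed-rank test on the differences as a sensitivity analysis.
- **If the sponsor prefers to switch on the differences:** write *will* instead of *may*, and note that the signed-rank test assumes symmetric differences. With one-sided skew and an unchanged mean, this switch gives type I error for the mean of 0.118–0.159 with no measurement error and 0.062–0.072 with error SD 0.5 per side. If the differences are symmetric under no effect, it stays at 0.051–0.055 and gains 3.4–5.1 power points over the t-test, again in a model without measurement error. Either route is defensible if it is fixed beforehand.

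The cost is two or three sentences and no new data. Keeping the t-test has a price when the differences are skewed: type I error can stay slightly raised (0.071–0.091 with no measurement error, 0.053–0.058 with error SD 0.5 per side).

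### SAP Section 2 wrongly treats equal test and control variances as a requirement of the paired t-test, and checks variance and normality on the groups instead of the within-pair differences

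*SAP*

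**What the plan says.** Section 2 has two screening rules. For normality, the Shapiro-Wilk test "will determine whether the data within each group approximate a normal distribution". For variances, an F-test compares the test group with the control group because equality is called a condition "which is an assumption necessary for parametric tests such as the paired samples t-test". The decision rule is: "Homogeneity of variance will be assumed if the F-test yields a P-value > 0.05".

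Section 3 sets the primary analysis without any condition: "a paired samples t-test will be conducted. This test is chosen due to the paired nature of data collected".

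Section 5, on additional analyses, opens with a sentence that mentions exploratory analysis and continues: "if data do not meet normality or variance assumptions, the following non-parametric tests may be applied as alternatives". Two entries follow. The Wilcoxon signed-rank entry reads "To compare medians between paired groups if normality assumptions are not met". The Levene entry reads "As an alternative check for homogeneity of variances, particularly if sample sizes are unequal".

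**The concern.** Three stated rules do not fit the paired design.

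- **The assumption is wrong.** A paired t-test is a one-sample t-test on the within-pair differences. It estimates one variance, that of the differences, and does not need the two marginal variances to be equal.
- **The variance checks are the wrong kind.** The F-test and Levene's test assume independent groups. Section 3 says each subject is observed under both conditions, so the two sets of values are expected to be correlated.
- **The normality check is on the wrong quantity.** The paired t-test needs approximately normal differences. Data can be skewed within each group while the differences are normal, for instance when a skewed subject effect is common to both conditions and cancels.

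What is at stake is the choice of test. Section 5 lists a failed variance assumption among its triggers and says 'may'. If that is read as applying to the primary comparison, a check with no bearing on the validity of the paired t-test could lead the analyst to change it after seeing the data.

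**Working it through.** **Inputs.** The 0.05 level is from SAP Section 1. The SAP does not state sidedness; two-sided is assumed. It gives no number of pairs, SD or correlation, so there is no stated figure to reproduce. Assumed ranges: n = 8 to 30 pairs, correlation ρ = 0, 0.5 or 0.8, test:control SD ratio 1, 1.5 or 2, bivariate normal pairs unless stated otherwise.

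**1. What the paired t-test needs.** With d the within-pair difference,

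t = mean(d) / (SD(d)/√n), and Var(d) = s₁² + s₂² − 2ρs₁s₂.

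With s₁ = s₂ = 1 and ρ = 0.5, Var(d) = 1 + 1 − 1 = 1. With s₁ = 1, s₂ = 2 and ρ = 0.5, Var(d) = 1 + 4 − 2 = 3. In both cases SD(d) is estimated directly from the differences, so t has n − 1 degrees of freedom under the null and the level is exact for normal differences. Simulation agrees: type I error was 0.048 to 0.052 over the assumed range. This step does not depend on the assumed n, ρ or SD ratio.

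**2. How the named checks behave on paired data.** Rejection rates at n = 20, 100,000 simulated trials per cell:

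| Setting | ρ = 0 | ρ = 0.5 | ρ = 0.8 |
|---|---|---|---|
| F-test, variances truly equal | 4.95% | 2.7% | 0.25% |
| Levene's test, variances truly equal | 5.4% | 3.3% | 0.55% |
| F-test, SD ratio 2 | 84% | 87% | 95% |

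With correlated pairs the checks do not hold their nominal 5%. At SD ratio 2 the F-test flags most trials, although the paired t-test is valid in all of them.

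**3. If every F-test flag led to the exact signed-rank test (mandatory gate).** Simulated with 40,000 trials per cell (Monte Carlo SE about 0.001 for type I error, 0.002 for power), type I error was 0.047 to 0.052, so there is no inflation. Power was set to 80% for the paired t-test. At SD ratio 2 and ρ = 0.5:

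| n | Flagged | Power, paired t | Power, gate | Loss (points) |
|---|---|---|---|---|
| 8 | 37.1% | 80.1% | 76.9% | 80.1 − 76.9 = 3.2 |
| 10 | 50.0% | 79.6% | 78.6% | 79.6 − 78.6 = 1.0 |
| 20 | 86.8% | 80.5% | 78.6% | 80.5 − 78.6 = 1.9 |
| 30 | 97.4% | 80.2% | 78.4% | 80.2 − 78.4 = 1.8 |

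Over all three correlations the loss at SD ratio 2 is about 3 points at n = 8 and 1 to about 2 points for n of 10 or more. It is at most 1.2 points at SD ratio 1.5 and 0.3 at ratio 1. The larger loss at n = 8 arises because the exact signed-rank test is conservative there: its attainable two-sided level is 2 × 5/256 = 0.039.

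**4. If the analyst may choose after a flag.** As a worst case, count a flagged trial as significant when either test is significant. At SD ratio 2, type I error is then about 0.050 to 0.055 at n = 8 to 10 and reaches 0.059 at n = 20 to 30.

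**5. Normality check.** With normal data, testing each group flags 9 to 11% of trials (two independent 5% checks would give 1 − 0.95² = 9.75%), against about 5% on the differences. With an assumed log-normal subject effect shared by both conditions, normal errors and ρ = 0.8:

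| n | Flag in either group | Flag on differences |
|---|---|---|
| 8 | 28% | 5–6% |
| 10 | 36% | 5–6% |
| 20 | 59% | 5–6% |
| 30 | 75% | 5–6% |

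Over the log-normal settings (ρ = 0.5 and 0.8) the paired t-test's type I error was 0.047 to 0.054 (Monte Carlo SE 0.003). The flags do not point to any failure of the test.

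**The case against.** The strongest case on the other side is that the primary test may never change. Section 3 commits to the paired t-test without condition. Section 5 concerns additional analyses, its opening sentence mentions exploratory analysis, and its Wilcoxon entry names non-normality only. A reader might infer from the words on variance assumptions that an F-test flag switches the primary test. The text allows that, but it is one of several readings and not the most specific one. This objection stands, and it limits the consequence. It does not make the Section 2 statement true or the checks suitable.

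A reader might also take the Levene entry's mention of unequal sample sizes as an error in itself, because complete pairs always give equal counts. That goes too far: Section 6 expects missing data, and nothing limits the variance check to complete pairs. The sound complaint about Levene's test is that it assumes independent groups.

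The sizes have no anchor in the SAP, because n, SD ratio and correlation are all assumed. The normality figures in particular depend on an assumed skewed subject effect, and they are flag rates, not losses of power or level. This is right, and it is a reason to rate the point low.

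Finally, replacing one pre-test by another is not an obvious gain. With exponential differences centred at mean zero and n = 20 to 30, a fixed rule that switches to signed-rank when Shapiro-Wilk on the differences gives P < 0.05 rejected about 12 to 16% of the time, against 7 to 8% for the t-test alone. Part of that arises because the signed-rank test does not target the mean under skew. So such a switch should not be required.

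**Conclusion.** The point holds and is minor. Section 2 states a false requirement for the paired t-test, checks it with independent-group tests, and tests normality on the groups instead of the differences. These are errors in the text whatever the sample size.

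The documents do not support the claim that a failed variance check will change the primary analysis; Section 5 leaves this open. Nor can one say flatly that type I error is safe. That holds for a mandatory F-test gate, which costs at most about 3 power points (SD ratio 2, n = 8). With free choice after a flag, type I error could rise to about 0.06 at SD ratio 2. All these sizes assume bivariate normal pairs, n = 8 to 30, correlation 0 to 0.8 and a two-sided 0.05 level.

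**What to change.** - Section 2: delete the Homogeneity of Variance paragraph. State that the paired t-test is applied to the within-pair differences and does not require equal test and control variances. Apply Shapiro-Wilk to the within-pair differences.
- Section 5: delete the Levene entry and the words 'or variance' in the opening sentence.
- Sections 3 and 5: remove the discretion in 'may' by naming the primary test in advance, for example the paired t-test as primary with the Wilcoxon signed-rank test as a sensitivity analysis. A fixed Shapiro-Wilk switch on the differences would also remove discretion, but it is an option and not a necessary part of the fix.

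The cost is SAP wording only. The variance tests are no longer run, and normality is tested once per outcome instead of once per group.

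### Section 4's Bonferroni rule is valid, but Holm's step-down procedure holds the same family-wise error, never rejects less and can reject more: a cheap, optional improvement

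*SAP*

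**What the plan says.** SAP Section 4 is conditional: "If multiple outcomes are analyzed simultaneously", then "the Bonferroni correction will be applied to adjust the significance threshold and control for the risk of Type I errors". It gives the calculation as follows: "The corrected P-value will be calculated by dividing the significance level (0.05) by the number of comparisons". This is single-step Bonferroni, in which every outcome faces the same bar of 0.05/k whatever the other outcomes show.

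The P-values come mainly from Section 3: "To compare outcomes between the test group and the control group, a paired samples t-test will be conducted". Section 5 allows the Wilcoxon signed-rank test as the alternative. Section 1 sets a level of 0.05 that "will be considered statistically significant for all tests". Section 7 adds that "P-values, confidence intervals (CIs), and effect sizes will be reported for primary and secondary outcomes", without saying whether the intervals are adjusted for multiplicity.

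The SAP states no number of outcomes, sample size, effect size or power target, and it does not claim that Bonferroni is the most powerful choice.

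**The concern.** Once one hypothesis in a family of k has been rejected, at most k − 1 true null hypotheses can remain if that rejection was correct, yet single-step Bonferroni still divides 0.05 by k. Holm's procedure relaxes the divisor at each step and keeps the same error guarantee. Where several outcomes have real effects, the rule in Section 4 can therefore leave some undeclared that Holm would declare at the same family-wise level.

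What is at stake is power on the second and later outcomes. Error control is not in question, and neither is the chance of finding at least one difference.

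A minor matter of wording sits in the same section. The quotient 0.05/k is a threshold, but the sentence that defines it calls it a P-value.

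**Working it through.** **1. The plan's own rule.** The only figures in the SAP are 0.05 and the instruction "dividing the significance level (0.05) by the number of comparisons". The thresholds sum to k × (0.05/k) = 0.05. With independent tests the family-wise error is 1 − (1 − 0.05/k)^k:

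| k | threshold 0.05/k | family-wise error |
|---|---|---|
| 2 | 0.025 | 0.0494 |
| 3 | 0.0167 | 0.0492 |
| 5 | 0.010 | 0.0490 |
| 10 | 0.005 | 0.0489 |

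The rule controls the error rate as stated.

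**2. Why Holm is never worse.** Holm orders the P-values and compares them in turn with 0.05/k, 0.05/(k−1), …, 0.05, stopping at the first failure. For k = 5 the bars are 0.0100, 0.0125, 0.0167, 0.0250 and 0.0500; Bonferroni uses 0.0100 throughout. Each Holm bar is at least 0.05/k, so every Bonferroni rejection is also a Holm rejection. For error control, let m₀ nulls be true. When the first true null is rejected, at most k − m₀ hypotheses have gone before it, so its bar is at most 0.05/m₀. The chance that any of the m₀ true nulls falls below that bar is at most m₀ × 0.05/m₀ = 0.05, whatever the dependence. In 200,000 simulated families per setting, no Bonferroni rejection was missed by Holm.

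**3. Size of the gain.** None of these inputs is in the SAP; all are assumed: 20 pairs, two-sided paired t-tests, true effect 0.8 SD of the paired difference, correlation 0.5 between outcomes, 20,000 simulated trials per setting.

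Check of the Bonferroni arm at k = 5: the noncentrality is 0.8 × √20 = 3.58, the critical value at two-sided 0.01 on 19 degrees of freedom is 2.861, and exact power is 75.4%. The simulation gives 75.1%.

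Average power per outcome when all effects are real:

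| k | Bonferroni | Holm |
|---|---|---|
| 3 | 81.9% | 89.0% |
| 5 | 75.1% | 85.7% |
| 8 | 68.7% | 81.9% |

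Varying one assumption at a time at k = 5:

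| Setting | Bonferroni | Holm |
|---|---|---|
| two of five effects real | 74.9% | 77.0% |
| one of five effects real | 75.7% | 75.8% |
| all real, correlation 0 | 75.6% | 88.8% |
| all real, correlation 0.9 | 75.1% | 82.3% |
| all real, effect 0.3 SD | 8.9% | 10.8% |
| all real, effect 1.2 SD | 98.9% | 99.9% |
| all real, 30 pairs | 93.9% | 98.0% |

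The chance of declaring all five of five goes from 42% to 72% at correlation 0.5. That is the most favourable summary, because it needs the same large effect on every outcome.

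**4. What does not change.** Holm's first bar is 0.05/k, so the chance of at least one rejection is identical. A second simulation (z tests, each effect sized for 80% power at unadjusted 0.05) shows this: for k = 3, all effects real and correlation 0, it is 96.0% under both methods. In that model the gain in average power with all effects real runs from about 5 points (k = 2, correlation 0.5: 71.2% to 76.5%) to about 11 points (k = 5, correlation 0: 58.9% to 70.4%; k = 10: about 50% to 61%). With one real effect it is about 0.2 points or less.

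**The case against.** The strongest reply is that nothing here is wrong: Bonferroni is a recognised method, it controls the error rate that Section 4 says it controls, and the plan makes no claim about power. That stands, so the point is an improvement and not a correction.

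A reader might infer that the plan gives up power for nothing. The documents do not support that. Section 7 promises confidence intervals, and Bonferroni offers simple simultaneous ones at level 1 − 0.05/k (99% for k = 5) that agree with its test decisions. Holm has no equally simple counterpart. Section 7 does not say that its intervals will be simultaneous, so the plan does not claim this advantage, but it is still a real cost of changing.

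A reader might also suppose that outcomes measured on the same subjects, and so correlated, make the case for Holm stronger. The figures run the other way: at k = 5 the gain falls from about 13 points at correlation 0 to about 7 at 0.9. The SAP lists no outcomes from which a correlation could be judged.

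Finally, the label given to 0.05/k might suggest a double correction, with adjusted P-values compared against an already adjusted threshold. Section 4 says that the correction acts on the threshold and never says that adjusted P-values will be set against it. Any power loss computed for double correction describes a plan that the SAP does not state; the wording is a labelling slip.

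**Conclusion.** The point holds as a cheap improvement to a valid rule. That Holm rejects at least as much as Bonferroni at the same family-wise 0.05 needs no assumption about this trial. The size of the benefit does. At k = 5 with 20 pairs, 0.8 SD and correlation 0.5, it is about 11 points of average power if all five effects are real, about 2 points if two are, and essentially nil if one is. The gain also shrinks when power is already very low or very high. The loss in this particular trial cannot be computed from the SAP.

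**What to change.** In Section 4, replace the Bonferroni rule with wording such as: Holm's step-down procedure will be applied across the k outcomes tested; ordered P-values are compared with 0.05/k, 0.05/(k−1), …, 0.05, stopping at the first failure; results are reported as Holm-adjusted P-values judged against 0.05. The adjusted value for the j-th smallest P-value is the largest, over i ≤ j, of (k − i + 1) × p(i), capped at 1. Delete the sentence that calls 0.05/k a P-value. Judging adjusted P-values against 0.05 also sits more easily with Section 1.

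In Section 7, label the confidence intervals as unadjusted 95% intervals and note that one may exclude zero where Holm does not reject.

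The cost is a few sentences in the SAP. No new data are needed, and the adjustment can be done by hand from the same P-values. Holm needs the same list of outcomes, and hence the same k, as Bonferroni; this change does not supply it. If intervals that match the test decisions matter more to the sponsor than the extra power, keeping Bonferroni is defensible, with 0.05/k relabelled as a threshold.

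### Does Section 5 misdirect the Wilcoxon signed-rank fallback by describing it as a comparison of medians?

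*SAP*

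**What the plan says.** Section 3 makes the paired t-test the primary analysis and gives the reason: "This test is chosen due to the paired nature of data collected, which allows for a direct comparison of each subject under different conditions". Section 5 lists the Wilcoxon signed-rank test as an alternative when the normality or variance assumptions are not met, with the purpose "To compare medians between paired groups if normality assumptions are not met". The normality check that leads there is the Shapiro-Wilk test of Section 2, which "will determine whether the data within each group approximate a normal distribution".

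On reporting, Section 7 allows a mean with SD or a "median and interquartile range (IQR) depending on the data distribution", and adds that "P-values, confidence intervals (CIs), and effect sizes will be reported for primary and secondary outcomes". It names no estimator for any test, the t-test included. Section 1 sets the threshold: "A significance level of $P < 0.05$ will be considered statistically significant for all tests".

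**The concern.** The signed-rank test works on within-pair differences. Its null hypothesis is that they are symmetric about zero, and its location measure is their pseudo-median, estimated by Hodges-Lehmann. The difference between two group medians is another quantity. The two agree when the differences are symmetric, as under a pure shift. They can part when the conditions differ in spread or skew.

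A reader who takes Section 5 at its word could therefore treat a significant result as evidence that the group medians differ. Section 7 might add to this: group medians and IQRs could be printed beside a P-value that concerns the differences, with no named estimate linking them. The Section 2 check looks at each group and not at the differences, so it does not show whether they are symmetric. At stake is what may be concluded from a significant fallback result.

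**Working it through.** The SAP gives no sample size, SD or effect on this point, so there is no figure of its own to reproduce. The only inputs from the document are the 0.05 threshold (Section 1), the pairing (Section 3), the within-group normality check (Section 2) and the stated purpose of the fallback (Section 5). Everything else below is assumed.

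**1. Can the test and the group medians disagree?** Yes, in a constructed example of seven pairs.

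- Control: 1, 2, 3, 10, 11, 12, 13 (median 10). Test: 3, 5, 7, 9, 16, 18, 60 (median 9).
- Shapiro-Wilk in the test group gives P = 0.004, so the normality check fails.
- Differences, test minus control: +2, +3, +4, -1, +5, +6, +47. The only negative difference has rank 1, so W- = 1 and W+ = 28 - 1 = 27.
- Of the 2^7 = 128 sign patterns, two have W- of 1 or less. Exact two-sided P = 2 × 2/128 = 0.031.
- Number of Walsh averages: 7 × 8/2 = 28. Their median, the Hodges-Lehmann estimate, is 4.0. The third lowest and third highest give the interval 1.0 to 26.0.

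The test favours higher values in the test group, although its median is the lower one.

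**2. How often could this matter?** The assumed model is bivariate lognormal pairs, both medians 1, log-scale correlation 0.5, so the group medians are equal and the median difference is exactly zero. There were 20,000 trials per cell, analysed with the exact two-sided signed-rank test at 0.05. The trigger is Shapiro-Wilk P < 0.05 in either group.

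| Log-SDs | Rejection, n = 10 / 20 / 30 | Rejection where the trigger fires |
|---|---|---|
| 0.4 vs 0.8 | 5.6 / 7.8 / 10.1% | 3.9 / 7.2 / 9.9% |
| 0.3 vs 0.8 | 6.1 / 9.0 / 12.1% | 4.2 / 8.1 / 11.7% |
| 0.3 vs 1.0 | 6.5 / 10.9 / 15.6% | 4.5 / 10.2 / 15.5% |
| 0.8 vs 0.8 (exchangeable) | 5.0 / 5.2 / 5.0% | 4.1 / 5.0 / 5.0% |

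The simulation standard error is at most 0.26 percentage points for the unconditional rates. A rerun with another seed agreed within simulation error. Significant results whose sample group medians do not point the same way as the Hodges-Lehmann estimate made up fewer than 0.2% of trials in every cell.

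Other assumed shapes can do worse. With a normal control and a shifted lognormal test group, equal medians and correlated pairs, rejection was 10% at n = 10 and 30% at n = 30 (3,000 trials each). There the pseudo-median of the differences is about 0.27, so the test is detecting a real feature of the differences.

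**3. Do the targets agree in the ordinary case?** With skewed outcomes, symmetric differences and a true shift of 0.5, the median difference is 0.50, the pseudo-median is 0.50 and the difference of group medians is 1.60 - 1.10 = 0.50.

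**4. What would rewording change?** The test statistic and P-value are computed from the same differences whatever the sentence says. The exact Hodges-Lehmann interval collects the shifts that this test does not reject, so it excludes zero when the test rejects. In the unequal-spread rows of the table it would exclude zero in the same samples, although the median difference is zero there.

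**The case for a change.** The strongest case for a change is that Section 5 states something incorrect about a test, which is more than silence, and that reading the sentence generously as the median difference does not rescue it: in the unequal-spread simulations that median is also zero, yet rejection exceeds 5% at 20 and 30 pairs. Section 5 also opens the fallback when the variance assumption fails, so the plan itself foresees unequal spread. With no estimator named, two analysts could report different quantities: a difference of medians, a median difference, Hodges-Lehmann or a rank correlation. Correcting this would cost one sentence.

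The statistical description stands: the sentence is imprecise. The rest carries less weight. Foreseeing a variance check is not evidence that the spreads differ, and the SAP gives nothing from which to judge the imbalance. The seven-pair example was built to show a reversal that is almost absent in simulation. Under Section 4, with as few as two comparisons, the threshold would be 0.05/2 = 0.025, and its P of 0.031 would not be significant. The missing estimator is a gap in detail that covers the t-test equally; Section 7 already commits to intervals and effect sizes, and several paired measures would honour that. The within-group normality check is a separate matter and adds nothing to this one.

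**Conclusion.** No change to the plan is called for. Section 5 uses a common loose description of a correctly chosen paired test. Read with Section 3, which rests the analysis on comparing each subject with itself, an analyst would run the test on within-pair differences and could meet the Section 7 commitment with a paired estimate and its interval, keeping group medians and IQRs as description.

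More exact wording would leave every P-value and every significance decision as it is. The excess rejection, up to 15.6% at 30 pairs in the lognormal cells and higher under the more extreme shape, depends on assumed differences in spread or shape and on assumed sample sizes. In the lognormal cells it disappears at 10 pairs once the normality check has failed, and with exchangeable groups rejection is about 5%. These rates describe the signed-rank test under asymmetric differences and do not demonstrate a fault in this trial's plan. What remains is a point of expression to bear in mind when results are written up: a significant fallback result speaks about the paired differences.
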